#### **13.6.2** Medication error

Medication error refers to any unintentional error in the dispensing or administration of an IMP.

Medication errors include accidental overdose or underdose, inappropriate schedule of product administration, incorrect route of product administration, wrong product administered, and expired product administered.

Accidental overdose or underdose where a clinical consequence occurred or could have occurred should be recorded based on investigator judgement.

Page 78 of 121

Inappropriate schedule of product administration where a clinical consequence occurred or could have occurred should be recorded based on investigator judgement.

Treatment non-compliance (including missed doses) where no clinical consequence occurred or could have occurred should not be recorded as medication errors. See Section 9.8.4 for recording of treatment compliance.

Medication error must be recorded on the other event involving IMP form in the eCRF. In addition, any clinical consequences of the medication error must be recorded as separate AEs on the AE form. If the AE originating from the medication error qualifies as an SAE, expedited reporting is required (Section 13.4).

#### 13.6.3 Misuse or abuse

The terms misuse and abuse are similar in that they both represent the intentional use of a drug in a way other than intended.

Misuse refers to situations where the IMP is intentionally and inappropriately used for therapeutic purposes not in accordance with the protocol.

Abuse refers to intentional use of an IMP for what could be considered desirable non-therapeutic effects (e.g., sedative, stimulant, euphoric effects).

Misuse and abuse must be recorded in the eCRF on the other event involving IMP form. In addition, any clinical consequences of misuse or abuse must be recorded as separate AEs on the AE form. If the AE originating from the misuse or abuse qualifies as an SAE, expedited reporting is required (Section 13.4).

# 13.6.4 Aggravation of condition

Any clinically significant aggravation/exacerbation/worsening of any medical condition(s) (including the trial disease), compared to screening, must be reported as an (S)AE in accordance with Sections 13.3 and 13.4.

As CHE is a fluctuating disease, consider to only report an AE if the aggravation/exacerbation exceeds normal disease fluctuation or if lesions appear in the area which is normally not affected by CHE.

Page 79 of 121

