### Reporting in eCRF

It will be recorded in the eCRF if vital signs were measured; if not, a reason should be provided. Vital signs (resting blood pressure, pulse, and body temperature) will be recorded in the eCRF. Any new clinically significant abnormal finding at the baseline visit will be recorded as an AE in the parent trial. Any clinically significant deterioration of a pre-existing condition recorded in the parent trial, as well as any new clinically significant sign, symptom, or illness occurring after the baseline visit will be recorded as an AE in accordance with Section 13.3.

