## Reporting in eCRF

At the visits indicated in the schedule of trial procedures (Section 4), the site staff will record in the eCRF if a blood sample was taken. If not, a reason should be provided. The investigator's assessment of the results ('normal', 'abnormal, not clinically significant', 'abnormal, clinically significant') will be recorded in the eCRF.

It will be recorded in the eCRF if a urine dipstick test was performed and whether urinalysis is required for further assessment, as judged by the investigator. If the urine sample was not tested with a dipstick, a reason will be provided. The investigator's assessment of the urine dipstick results ('normal', 'abnormal') will be recorded in the eCRF. In case urinalysis is performed, the investigator's assessment of the results ('normal', 'abnormal, not clinically significant', 'abnormal, clinically significant') will be recorded in the eCRF.

It will be recorded in the eCRF if the subject is a woman of childbearing potential and if a urine pregnancy test was performed. If not, a reason should be provided. Also, the date and the outcome of the urine pregnancy test will be recorded in the eCRF ('positive', 'negative').

Clinically significant abnormal laboratory results at the screening visit will be documented as medical history in the eCRF. At the baseline visit, any clinically significant deterioration of a pre-existing condition will be reported as an AE in the parent trial. Any new clinically significant sign, symptom, or illness occurring after baseline will be reported as an AE in accordance with Section 13.3.

Page 66 of 121

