# 13.2 Collection of adverse event reports

AE data must be collected from time of first trial-related activity after the subject has signed the informed consent form (ICF) until end of trial (as defined in Section 7.3). To avoid duplicate reporting of AEs for subjects rolling over from a parent trial, any AE with onset prior to or at the baseline visit in the extension trial should be recorded as an AE in the parent trial. If ongoing at the baseline visit for this extension trial, the AE will be transferred to the extension trial as part of the subject's medical history. If such an ongoing AE worsens after the baseline visit in this extension trial, the AE should be recorded as a new AE in the extension trial. An AE with onset after the baseline visit in this extension trial and until end of trial for the individual subject (defined as attending the last visit in the trial) will be recorded as an AE in the extension trial.

AEs must be assessed by a physician.

At all visits, the subject will be asked a non-leading question by the investigator about AEs, e.g.: "How have you felt since I saw you last?" Subject-reported local tolerability will be queried specifically (see Section 11.5.4) and reported as AE(s) if deemed relevant by the investigator. In case of suspected local skin reaction related to IMP application, the final diagnosis based on the IMP patch test result (see Section 11.5.4.1) must be recorded as an AE. If the AE qualifies as an SAE, expedited reporting is required (Section 13.4). It is important that the investigator also observes the subject for any changes not reported by the subject and records these changes.

Refer to Sections 11.5.1 to 11.5.5 for principles for data entry in the eCRF.

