#### 14.3.8.1 Adverse events

AEs will be coded during the course of the trial according to Medical Dictionary for Regulatory Activities (MedDRA). AEs will be presented by preferred term and primary system organ class (SOC).

AEs with onset after baseline visit will be considered treatment-emergent. AEs reported as ongoing at baseline in this trial will be reported as medical history. Any worsening of an ongoing AE after baseline visit will be recorded as a new AE in this trial. In each of the tabulations, AEs will be defined by MedDRA preferred terms within primary SOC. New AEs recorded after end of trial will be presented in a listing.

AEs will be summarised in terms of the number of subjects with at least 1 event, the percentage of subjects with at least 1 event, the number of events, and the event rate per 100 person years of observation time.

Related AEs are defined as AEs for which the investigator has not described the causal relationship to IMP as 'not related'.

An overall summary presenting any treatment-emergent AEs, deaths, SAEs, premature discontinuations from IMP and/or withdrawals from the trial due to AEs, treatment-related AEs, and severe AEs will be given.

Tabulations by SOC and preferred term will be presented for all AEs, SAEs, related AEs, AESIs, AEs leading to withdrawal from trial, and AEs leading to permanent discontinuation of IMP. In addition, all AEs will be presented by severity and causal relationship to IMP,

Page 85 of 121

respectively. If an AE worsens in severity, the severity will be reported as the most severe recording for that AE.

SAEs and pregnancy occurrences will be evaluated separately, and a narrative will be given.

AESIs will be listed. No narratives will be given.

AEs leading to withdrawal from trial or permanent discontinuation of IMP will be listed. The detailed listing will provide an overview of the individual cases and include the age and sex of the subject, if the subject was on treatment with IMP at the time of AE onset, the AE preferred and reported terms, causality and severity of the AE, the action taken with the IMP, AE outcome, start and stop date of AE, duration of AE, and number of days since first and last IMP administration. No narratives will be given.

AEs will be summarised by treatment status (on/off treatment) at the time of onset. Treatment status will be derived from IGA-CHE data..

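### Section 13.6.4 judges worsening against screening, while the trial's AE rules use the baseline visit, so some post-baseline worsening need not be reported

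*Combined protocol and SAP*

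**What the plan says.** Section 13.6.4 (Aggravation of condition) covers clinically significant worsening of any medical condition and names the trial disease explicitly. Such worsening, "compared to screening, must be reported as an (S)AE in accordance with Sections 13.3 and 13.4". For CHE the next sentence gives the investigator latitude: "consider to only report an AE if the aggravation/exacerbation exceeds normal disease fluctuation", or if lesions appear where the subject is not normally affected.

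The other AE rules use the baseline visit:

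- Section 13.2, earlier events: "any AE with onset prior to or at the baseline visit in the extension trial should be recorded as an AE in the parent trial".
- Section 13.2, events carried over as medical history: "If such an ongoing AE worsens after the baseline visit in this extension trial, the AE should be recorded as a new AE".
- Section 14.3.8.1, the analysis: "AEs with onset after baseline visit will be considered treatment-emergent", and "Any worsening of an ongoing AE after baseline visit will be recorded as a new AE in this trial".

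The primary endpoint (Section 6, Panel 3) is the number of treatment-emergent AEs from baseline to Week 38.

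Notes 1 and 5 to Panel 2 place screening ideally at the parent trial's Week 12 visit. It may be as early as Day -34, or on the same day as baseline (parent Week 16). Under Section 9.3.1, subjects with IGA-CHE 0 or 1 at baseline are taken off treatment.

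**The concern.** One rule decides whether a worsening has to be reported, and another decides whether a reported event counts in this trial. They use different visits. Treatment-emergence is a rule about onset dates, so it can only act on events that have already been reported. If 13.6.4 does not call for a report, nothing reaches the primary endpoint.

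The mismatch matters most for a subject who does well late in the parent trial, stops treatment at baseline and then deteriorates. In an as-needed regimen, worsening after stopping is a natural safety question. The trial has no control arm, so uneven case-finding across about 110 sites cannot be offset by a comparison. Section 14.3.8.1 also summarises AEs by on- and off-treatment status, and any under-recording of off-treatment worsening would show there directly.

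**Working it through.** No power, alpha or sample-size figure bears on this point. The check is a comparison of rules plus a count of possible patterns.

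**1. Gap between the two reference visits.** The nominal gap is 28 days, with a 3-day window at each of parent Weeks 12 and 16: 28 + 3 + 3 = 34 days. This agrees with the 34 days in note 5 to Panel 2. The minimum is 0 days, when both visits fall at parent Week 16.

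**2. Condition for a loss.** Let s, b and p be severity at screening, at baseline and at a later visit. Worsening since baseline means p > b. Worsening since screening means p > s. The two rules disagree, with a loss, when b < p ≤ s. This requires improvement between screening and baseline (b < s).

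**3. Count for subjects stopped at baseline.** IGA-CHE serves as a stand-in for severity here; 13.6.4 itself does not use it. Take s = 0 to 4, b = 0 or 1, and p = 2 to 4, which gives 5 × 2 × 3 = 30 patterns.

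| Screening s | Later scores p not worse than s | Patterns (× 2 values of b) |
|---|---|---|
| 0 or 1 | none | 0 |
| 2 | 2 | 2 |
| 3 | 2, 3 | 4 |
| 4 | 2, 3, 4 | 6 |
| Total | | 12 |

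All 30 patterns are worse than baseline. Only 30 − 12 = 18 are worse than screening. If the two visits coincide (s = b), none is lost.

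**4. Which screening is meant.** Section 13.6.4 does not say. Section 11.2 also transfers parent-trial screening and baseline data into this trial. If parent screening were meant, and IGA-CHE there is assumed to be 3 or 4 (the parent trials enrolled moderate to severe CHE), there are 2 × 2 × 3 = 12 patterns. Of these, (2 + 3) × 2 = 10 are not worse than screening.

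These are counts of possible patterns, not expected frequencies. The documents give no distribution of change from Week 12 to Week 16, so they cannot be turned into a number of AEs.

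**5. Which conditions other rules already protect.**

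- AEs ongoing at baseline: protected by 13.2 and 14.3.8.1.
- Findings on vital signs, physical examination and ECG: Sections 11.5.1 to 11.5.3 make an AE of "Any clinically significant deterioration of a pre-existing condition recorded in the parent trial", without reference to screening.
- Other pre-existing conditions: Appendix 1 counts their clinically significant worsening as an AE, but names no reference visit.
- CHE: 13.6.4 is the only section that sets a specific rule.

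What remains exposed is mainly CHE, together with medical-history conditions that are not ongoing AEs and that improved between the two visits.

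**The case against.** The strongest reply is that 13.6.4 states what must be reported and does not bar other reports. Appendix 1 already makes worsening of pre-existing conditions an AE, and 13.2 places any AE with onset after baseline in this trial. An investigator following those two rules would report a non-CHE condition that worsens after baseline, whatever its state at screening. That largely stands. It does not remove the conflict, because Appendix 1 is silent on the reference visit and 13.6.4 is the section that supplies one.

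For CHE, the reply is that the fluctuation sentence decides most cases. A return to the level of at most 34 days earlier may well be ordinary fluctuation and go unreported under either reference visit. This stands too, and it limits what the change can achieve. CHE relapse also remains visible in IGA-CHE, HECSI, the time to first IGA-CHE ≥2 and the number of on-treatment periods, although none of these feeds the primary endpoint.

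A reader might infer three stronger things that the documents do not support:

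- **Double counting.** A condition that worsened between Weeks 12 and 16 and then stayed stable is still worse than screening, so it might seem to need a second report. Section 13.2 assigns events with onset up to and at baseline to the parent trial, and 14.3.8.1 counts only onset after baseline. A stable condition therefore does not enter the endpoint.
- **Lost laboratory events.** For laboratory results, Section 11.5.5.2 says "Any new clinically significant sign, symptom, or illness occurring after baseline will be reported as an AE" and omits post-baseline deterioration of a pre-existing condition. Appendix 1 already covers such worsening, and any laboratory abnormality that the investigator judges clinically significant. The omission is editorial.
- **A large affected group.** The phase 2b response rates (39.0% and 10.5%), with an assumed parent allocation of 1:1 to 2:1, suggest that (39.0 + 10.5)/2 = 24.75% to (2 × 39.0 + 10.5)/3 = 29.5% of subjects are off treatment at baseline. That is the size of the group, not the share with a missed event. A loss also needs improvement since screening, later worsening that is clinically significant and beyond fluctuation, and a level no worse than screening.

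**Conclusion.** The conflict is real in the current text. Section 13.6.4 refers to screening, whereas Sections 13.2 and 14.3.8.1 refer to the baseline visit. Worsening after baseline that does not pass the screening level falls outside 13.6.4, although it is the kind of event the primary endpoint is meant to count.

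The effect is confined mainly to CHE and to conditions that are not ongoing AEs, in subjects who improved between screening and baseline. Its size cannot be estimated from the documents and is probably small, because Appendix 1, Section 13.2 and the fluctuation sentence each cover or override part of it. This conclusion assumes that sites read 13.6.4 literally as their rule for worsening. It does not show that the AE count would be materially wrong. The text should be corrected because the section concerns the primary endpoint and the correction is cheap.

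**What to change.** In Section 13.6.4, replace *compared to screening* with *compared to the baseline visit in this trial*, so that it agrees with Sections 13.2 and 14.3.8.1. Keep the normal-fluctuation sentence unchanged. This also removes the doubt about which screening is meant.

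Optionally, for editorial consistency, give the laboratory text in Section 11.5.5.2 the same statement on post-baseline deterioration that Sections 11.5.1 to 11.5.3 carry.

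The cost is one wording change (two with the optional edit) and a note to sites, with no new data or visits. The small downside is that some expected relapses in subjects clear or almost clear at baseline will now need the investigator's judgement on whether they exceed normal fluctuation.

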#### 13.7 Follow-up for final outcome of adverse events

During the trial, the investigator should follow up for final outcome on all AEs (including SAEs). Once a subject leaves the clinical trial, the investigator should follow up on the outcome of all non-serious AEs classified as possibly or probably related to the IMP until the safety follow-up visit or until the final outcome is determined, whichever comes first. Non-serious AEs classified as not related to the IMP do not need to be followed up for the final outcome after the subject leaves the trial. The safety follow-up will be performed as a phone visit and may be delegated to site staff as per the signature and designation of responsibility log, provided the personnel is trained in AE reporting.

All SAEs must be followed up until a final outcome has been established, that is, the follow-up may continue beyond the end of the clinical trial. For SAEs which have stabilised and from which the subject cannot be expected to recover during the trial or the safety follow-up periods, e.g. chronic or stabilised conditions, the final outcome at the investigator's discretion should be reported as 'recovering/resolving' or 'not recovered/not resolved'. In addition, a statement detailing why the subject cannot be expected to recover during the trial, e.g. that the SAE has stabilised or is chronic, should be added to the narrative description of the SAE on the SAE form.

Any pregnancy occurring during the trial will be followed up as described in Section 13.5.1.

#### 13.8 Handling of an urgent safety measure

An urgent safety measure is a measure taken to implement an action/protocol deviation under an emergency. This is defined as "...the occurrence of any new event relating to the conduct of the trial or the development of the investigational medicinal product where that new event is likely to affect the safety of the subjects, the sponsor and the investigator shall take appropriate urgent safety measures to protect the subjects against any immediate hazard." (43).

If the investigator becomes aware of information that requires an immediate change in a clinical trial procedure or a temporary halt of the clinical trial to protect clinical trial subjects from any immediate hazard to their health and safety, the investigator can do so without prior approval from LEO Pharma, regulatory authorities, or IRBs/IECs.

The investigator must immediately inform LEO Pharma – by contacting the clinical project manager or medical expert – of this change in a clinical trial procedure or of the temporary

Page 80 of 121

halt; the investigator will provide full details of the information and the decision-making process leading to the implementation of the urgent safety measure.

LEO Pharma must act immediately upon receipt of the urgent safety measure notification in accordance with internal procedures and local legislation.

Page 81 of 121

#### 14 Statistical methods

## 14.1 Sample size

The expected sample size for this trial is approximately 600 subjects. No formal sample size has been calculated, as the primary objective for the trial is to evaluate safety, which is reflected by the open-label trial design. No comparative analyses are performed in this trial. The expected sample size is based on the population size of the parent trials (920 subjects) and assumptions regarding completion rates in the parent trials.

The aim is to have sufficient exposure for an adequate safety evaluation of long-term treatment according to the ICH E1 guideline. The target is a minimum of 300 subjects completing 6 months and 100 subjects completing 12 months of treatment with delgocitinib, respectively. Six months of treatment is defined as 16 weeks of twice-daily delgocitinib cream 20 mg/g plus 10 weeks with twice-daily delgocitinib cream 20 mg/g as needed treatment, or cream vehicle (in the parent trial) plus 26 weeks with twice-daily delgocitinib cream 20 mg/g as needed treatment. Similarly, 12 months of treatment is defined as 16 weeks of twice-daily delgocitinib cream 20 mg/g as needed treatment.

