# 1 Protocol synopsis

Trial ID	LP0133-1403	
EudraCT no.	2020-002962-15	
Title of trial	A phase 3 extension trial of DELTA 1 and DELTA 2 to evaluate the long-term safety of a twice-daily treatment with delgocitinib cream 20 mg/g as needed for up to 36 weeks in adult subjects with chronic hand eczema (DELTA 3)	
Short title of trial	An open-label multi-site extension trial LP0133-1401 (DELTA 1) or LP0133-1	
Main objectives	Objectives	Endpoints
and endpoints	Primary objective:	Primary endpoints:
	To evaluate the long-term safety of an as-needed treatment with twice-daily applications of delgocitinib cream 20 mg/g.	Number of treatment-emergent AEs from baseline up to Week 38.
	Secondary objective:	Secondary endpoints:
	To evaluate the long-term efficacy of an as-needed treatment with	• IGA-CHE  score at each scheduled visit from baseline up to Week 36.
	twice-daily applications of delgocitinib cream 20 mg/g.	• IGA-CHE score of 0 (clear) or 1 (almost clear) at each scheduled visit from baseline up to Week 36.
		• HECSI  score at each scheduled visit from baseline up to Week 36.
		• HECSI-75 at each scheduled visit from baseline up to Week 36.
		HECSI-90 at each scheduled visit from baseline up to Week 36.
1) The IGA-CHE is an instrument used in clinical trials to rate the global chronic hand eczema (CHE) and is based on a 5-point sca to 4 (severe).		
	(erythema, infiltration/papulation, vesicle	ical trials to rate the severity of 6 clinical signs es, fissures, scaling, and oedema) and the extent (fingertips, fingers [except fingertips], palm of of standard scales.
Abbreviations: AE = adverse event; HECSI = Hand Ecz least 75% improvement in HECSI score from baseline in improvement in HECSI score from baseline in parent trial. Assessment for chronic hand eczema.		aseline in parent trial; HECSI-90 = at least 90%
Final collection of data for the primary endpoint	Week 38	
Trial design	Subjects who completed the treatment period in the parent trials (LP0133-1401 or LP0133-1402) will be offered the opportunity to participate in this extension trial. In the parent trials, subjects were treated either with delgocitinib cream 20 mg/g or cream vehicle twice daily for 16 weeks.	

Page 15 of 121

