# 7 Trial design

# 7.1 Overall trial design

This trial is a phase 3, open-label, multi-site, extension trial. The trial is designed to evaluate the long-term safety of twice-daily applications of delgocitinib cream 20 mg/g as needed in eligible subjects with CHE who completed one of the 2 pivotal phase 3 trials with delgocitinib cream 20 mg/g or cream vehicle (parent trials – LP0133-1401 or LP0133-1402). The trial will include a screening period of up to 4 weeks (Week -4 to Week 0) and a treatment period of 36 weeks during which subjects will be treated with delgocitinib cream 20 mg/g twice daily as needed. During the treatment period, subjects will attend site visits every 4 weeks; if needed, unscheduled visits will be performed to initiate or stop treatment with delgocitinib cream 20 mg/g twice daily. Subjects will attend an end-of-treatment visit at Week 36 and a safety follow-up will be performed by phone approximately 2 weeks after the end-of-treatment visit to assess any AEs. The trial design is illustrated in Panel 1.

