# 14.3.11 Analysis of data to support submission for marketing authorisation approval

To support submission for marketing approval, analyses of data will be performed once sufficient exposure (defined in section 14.1) is available to evaluate the long-term safety of delgocitinib cream 20 mg/g. Results of these analyses will be included in a preliminary clinical trial report.

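### As it reads, Section 14.1 sets '12 months of treatment' at 16 as-needed weeks, less than its own 26-week '6 months', and the Section 14.3.11 analysis trigger relies on it

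*Combined protocol and SAP*

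**What the plan says.** Section 14.1 reports no formal sample size calculation. It expects about 600 subjects from parent trials of 920, and judges long-term exposure against ICH E1: "The target is a minimum of 300 subjects completing 6 months and 100 subjects completing 12 months of treatment with delgocitinib, respectively".

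It then defines both durations. Six months is reached by one of two routes. A subject on delgocitinib in the parent trial needs those 16 weeks plus 10 as-needed weeks here. A subject on vehicle needs "cream vehicle (in the parent trial) plus 26 weeks with twice-daily delgocitinib cream 20 mg/g as needed treatment". The next sentence is the 12-month definition: "Similarly, 12 months of treatment is defined as 16 weeks of twice-daily delgocitinib cream 20 mg/g as needed treatment". It names no parent-trial component and no parent arm. No other section defines 12 months of treatment.

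The periods themselves are clear elsewhere. The synopsis says: "In the parent trials, subjects were treated either with delgocitinib cream 20 mg/g or cream vehicle twice daily for 16 weeks". Section 7.1 gives this trial "a treatment period of 36 weeks during which subjects will be treated with delgocitinib cream 20 mg/g twice daily as needed".

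Section 14.3.11 makes the definition operational: "analyses of data will be performed once sufficient exposure (defined in section 14.1) is available to evaluate the long-term safety". Those results go into a preliminary clinical trial report, and Appendix 3D plans two database locks to support the submission.

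**The concern.** A 12-month threshold cannot sensibly be lower than the 6-month threshold beside it. The 6-month definition treats the two parent arms separately, because they enter with different prior exposure. The 12-month sentence drops that distinction, although it matters more there: one arm can reach a year within the programme and the other cannot.

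The 300 and 100 counts are the plan's stated test of adequate long-term exposure, and half of that test rests on this sentence. If it were applied as it reads, the preliminary report could count as 12-month subjects people whose time on the delgocitinib regimen is well short of a year.

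**Working it through.** All durations are weeks under the assigned regimen. In the extension this means weeks of as-needed treatment, not weeks of actual application.

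**Inputs**
- Parent-trial treatment: 16 weeks, delgocitinib or vehicle (synopsis).
- Extension treatment: 36 weeks as needed (Section 7.1).
- Six-month definition: 16 + 10 weeks, or vehicle + 26 weeks (Section 14.1).
- Twelve-month definition as it reads: 16 weeks as needed (Section 14.1).
- Targets: 300 and 100 subjects; about 600 expected (Section 14.1).

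**1. Reproduce the 6-month figure.** Former delgocitinib: 16 + 10 = 26. Former vehicle: 0 + 26 = 26. Half a year is 365.25 / 7 / 2 = 26.1 weeks. Both routes agree.

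**2. Try the 12-month figure.** A year is 365.25 / 7 = 52.2 weeks. The sentence gives 16.
- Against its own 6 months: 26 − 16 = 10 weeks shorter.
- Against 52 weeks: 16 / 52 = 0.31.

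The figure does not reproduce. Crediting the parent-trial weeks as well gives 16 + 16 = 32, still not 52.

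**3. What the design allows.** Former delgocitinib: 16 + 36 = 52 weeks. Former vehicle: 0 + 36 = 36 weeks. Only the first sum reaches 12 months.

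**4. When a subject would count, in extension weeks**

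| Parent arm | 6 months | 12 months, literal | 12 months, 16 + 36 |
|---|---|---|---|
| Delgocitinib | Week 10 | Week 16 (32 weeks in total) | Week 36 (52 in total) |
| Vehicle | Week 26 | Week 16 (16 weeks in total) | not attainable |

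On the literal text a former vehicle subject reaches '12 months' 26 − 16 = 10 weeks before reaching '6 months'. A former delgocitinib subject counts 36 − 16 = 20 weeks before 52 weeks is possible.

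**5. When the trigger would fire.** The literal text still imposes two conditions: 300 subjects at 26 weeks, and 100 subjects with 16 as-needed weeks. Which is met last depends on accrual.
- Illustration: if 300 former delgocitinib subjects entered on one day, the first condition would be met at Week 10 and the second only at Week 16, with none of them at 52 weeks.
- With staggered entry, early entrants could already have passed Week 36 when the later condition is met.

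The documents give no accrual schedule, so no trigger date can be computed.

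**6. Is the 52-week target attainable?** The parent allocation ratio is not given. Assume 600 roll over in proportion to it:
- 1:1 gives 300 former delgocitinib subjects, so 100 / 300 = 33% must complete Week 36.
- 2:1 gives 400, so 25%.
- 3:1 gives 450, so 22%.

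Correcting the definition leaves room to meet the target across this range.

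**The case against.** The strongest objection is that the plan may not contain this definition. In Section 14.1 parent treatment is described as weeks 'of' the cream and extension treatment as weeks 'with' it. The 12-month sentence opens in the first style and closes with the as-needed ending of the second. That is what would remain if the words between two identical phrases were skipped, and 'Similarly' announces the same parent-plus-extension structure. The text was read from PDF by a program and is visibly damaged in places, such as the amendment history in Appendix 10. If the words were lost there, the plan has no error. This stands, and the text alone cannot settle it.

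The intended meaning is also easy to infer. The section cites ICH E1, sets separate 6- and 12-month targets, and sits in a 16 + 36 week programme. No endpoint or analysis set uses the definition, and correcting it leaves the expected 600 unchanged. Section 14.3.3 reports days of exposure, which would expose a short duration, though only for this trial and not for the parent weeks. These points reduce the likely harm. They do not supply a usable definition for the trigger.

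A reader might go further and infer that the only binding condition is 300 subjects at 26 weeks, met at extension Week 10; that the report would be triggered with nobody at 12 months; or that this was planned. The documents support none of these. The literal text still requires 100 subjects at 16 as-needed weeks. An absence of 52-week subjects is one possibility under unknown accrual. The ICH E1 aim and the programme length point to a wording slip.

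**Conclusion.** The point holds on the text as it reads, subject to a check of the source. The stated 12-month threshold is 16 weeks where the plan's own periods give 52. It is 10 weeks below the plan's 6-month threshold, and it is not limited to the one parent arm that can reach a year. For an individual subject the literal rule advances '12 months' by 20 weeks (former delgocitinib), or grants it where at most 36 weeks are possible (former vehicle).

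The internal contradiction needs no assumption beyond the text being complete. That is the one uncertainty, so confidence is high about the sentence as read and conditional about the plan. The effect on the trigger date cannot be sized without accrual data. If the sentence stands in the source, it should be corrected before the Section 14.3.11 count is made or reported.

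**What to change.** First compare the sentence with the source PDF. If a parent-plus-extension term is present there, nothing needs changing in the duration; confirm only that the restriction by parent arm is clear.

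If the sentence stands, replace it with a definition that:
- gives the two components separately: 16 weeks on delgocitinib cream 20 mg/g in the parent trial, then 36 weeks of as-needed treatment in this trial, 52 weeks in all;
- says that only subjects randomised to delgocitinib in the parent trial can qualify;
- counts a subject on completion of the Week 36 visit. Panel 2 allows ±3 days around Day 253, so an in-window visit on Day 250 falls 249 days after Day 1, against 36 × 7 = 252. A strict day count could therefore drop subjects who completed on schedule.

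Apply the same definition to the Section 14.3.11 trigger.

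The cost is one sentence in the protocol or SAP. The 12-month count will be lower and available later than under the literal text. Counting by parent arm needs the parent allocation, which Section 5.3 keeps concealed while the parent trials are ongoing, but the 6-month definition already carries that need.
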